Title:

Young Adults' Responses to E-Cigarette Advertisement Features and the Effect of Restricting Features on Tobacco Use - Phase 2

NCT: NCT05207033**Date:** 4/3/2025

Study Protocol:
RESEARCH DESIGN
R00 Phase: Aim 2:

Participant Recruitment and Screening. We will recruit 150 young adults susceptible to EC use to complete the study. Participants will be recruited from the greater Worcester area using email, flyers, and social media, advertising an opportunity to participate in a health messaging study. Inclusion criteria are as follows: 1) 18 years old, 2) fluent in English (earn a score of at least 4 on the Rapid Estimate of Adult Literacy in Medicine), 3) biochemically confirmed abstinence of alcohol (breath alcohol concentration=.00) and combusted tobacco or marijuana (eCO: exhaled carbon monoxide <6 parts per million) at time of visit, and 4) reporting never trying an e-cigarette, not even a puff. Susceptibility to EC use, will be determined using the Susceptibility to Use Tobacco Products questionnaire.¹³

In the R00 Phase, I will use the knowledge gained in the K99 to determine the highest impact features of the selected EC ads. The highest impact features will be determined by a host of variables including features that receive the greatest visual attention (determined by eye-tracking), orienting response (determined by deceleration of heart rate), and arousal (determined by increased skin conductance). Self-report measures will be considered as well including ads associated with increased acceptance, higher positive attitudes, decreased EC severity, and increased behavioral intentions. From this information, I will create two conditions of advertisements: 1) regulated advertisements and 2) unregulated advertisements. Regulated advertisements will be the same 15 advertisements as Study 1 but with the omission of the high impact features as a way to simulate effects that may occur in young adults if these high impact features were restricted by the FDA. Unregulated advertisements will be kept in their true form with no manipulation. Using an RCT, I will track participant changes over 6 months in the following measures: susceptibility, severity, behavioral intentions, and actual tobacco use behavior following exposure to EC ads.

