Participant Screening and Recruitment. Participants will be screened and recruited in the same fashion as Study 1. If participants meet eligibility, they will be scheduled for a visit. The inclusion criteria will remain the same as in Study 1. The sample will include young adults who are susceptible to using ECs.²⁰ To account for an anticipated attrition rate of 20%, 150 participants will be recruited to ensure a sample of 120 participants. *Note: Participants will be offered information about the Massachusetts Tobacco Cessation and Prevention Program (MTCP).*

Retention. All participants will receive \$5 per visit to offset travel costs to and from the study site for a total of 4 visits (\$20), \$25 for each visit that they attend (\$100), and an additional \$1 for each time they open the online magazine and answer the survey questions (\$24), for a total of \$168. We will also facilitate study visits by offering evening and weekend appointments as well as additional retention strategies (e.g., multiple sources of contact, reminder calls/emails/texts). These methods are consistent with our team's previous studies and have resulted in excellent retention rates.

Procedures. Following confirmation of eligibility criteria and demonstration of participants' informed consent, participants will come to the lab for a baseline visit and complete sociodemographic questions and measures pertaining to tobacco use susceptibility,²⁰ perceived severity of using ECs,²¹ motivations to avoid ECs,²² behavioral intentions,²³ exposure to tobacco advertising,^{24,25} and receptivity to tobacco advertising.²⁶ Participants will also receive a tutorial on how the online magazine will work. Then, participants will be randomized in a 1:1 ratio to one of two conditions using a computer-generated sequence: 1) Regulated condition in which all features that are highest impact have been removed or 2) Unregulated condition in which all features remain in the advertisements. Research staff will be blinded to condition allocation. Advertisements will be the same as in Study 1 but manipulated for the regulated condition. Every week, for 24 weeks, participants will be instructed to view a 10-page online magazine

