delivered via email that includes content and articles aimed at young people from popular magazines among young adults, such as ESPN Magazine and Marie Claire that often contain EC ads.⁷ Before viewing, participants will be asked about their exposure to tobacco advertising in the last week and their receptivity to advertising as well as other masking questions. Every magazine will also contain two EC ads and two ads for products other than tobacco. During viewing, time spent on the ad page will be recorded. Every week, the online magazine will contain different content. Additionally, EC ads will be repeated at times. Opening and reading of the online magazine will be validated using recall tasks and incentives. At the one month, three month, and six month marks, participants will come into the lab and be assessed for tobacco use susceptibility,²⁰ perceived severity,²¹ motivations to avoid ECs,²² behavioral intentions to use EC, and recall of the ads.²³ Participants will also be asked about their tobacco use, including ECs²⁴ and bio-markers of EC use, in addition to eCO to confirm self-reported combusted tobacco use status. See Study 2 Flow Chart.

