Measures. Sociodemographic data will assess participant age, sex, marital status, ethnicity, employment status, occupation, years of education, and socioeconomic status. Time spent on ad will be measured by a timer that records the amount of seconds a participant spends on the EC ad through REDCap. Tobacco use questions including pictures to enhance recall will assess tobacco use across all tobacco products (i.e., cigarettes, cigars, cigarillos, little cigars, hookah, pipe tobacco) including ECs.²⁴ Tobacco use susceptibility, including ECs susceptibility of use will be measured using the 27-item measure.²⁰ Perceived severity of using ECs will be assessed by participants' perceived significance, severity, and seriousness of health threats from EC use.²¹ Motivation to avoid ECs including importance, confidence, and readiness to avoid ECs will be collected to assess for changes in motivations.²² Behavioral intentions²³ will be evaluated using questions like "How interested are you in trying ECs?" and "How willing are you to try ECs?" Participants will also complete the PhenX Toolkit measure of participants' exposure to tobacco advertising^{24,25} and tobacco advertising receptivity, a validated measure of tobacco promotional product influence.²⁶ Biochemical confirmation of tobacco non-use will be conducted with salivary cotinine (~3 day nicotine biomarker).

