Power Analysis. Trial of EC products is the primary outcome of the study; thus estimated power will be based on this outcome at the 6-month follow-up. No direct data is available on which to base sample size estimates. The closest estimates for the trial of EC products among unregulated and regulated groups are based on a study conducted by [name] (co-mentor) examining EC trial rates at 6-month follow-up (7.9% vs. 4.7% respectively) among young adults who were exposed vs. not exposed to 4 EC ads at a single time point.⁵ Since participants will be shown 24 ads over 6 months, we estimate that the trial of EC products after viewing EC advertisements over multiple time points will be higher in both the unregulated (24%) and regulated (6%) groups. As such, 150 participants (75/group) will be enrolled in the study. The sample size will provide 80% power to detect an 18% difference in increased trial of EC products between unregulated and regulated groups for a two-sided .05 level chi-squared test. Our estimates of sample size adjust for attrition rates of 20% in each arm. These attrition rates are a conservative estimate based on [name] (co-mentor) previous research. We are confident that with a total sample size of 150 participants (n = 120 after accounting for attrition), we will have adequate power to test our primary aim. It is important to note that this sample size is deliberately conservative, as it does not assume the availability of repeated outcome measures that will be taken throughout the study. By choosing models that utilize longitudinal data, we will be increasing the power to detect differences between arms. Note: We are currently running a trial that will help us work out any unforeseen issues with the study and sample size, but are basing these estimates on the best available data⁵ and most conservative estimates.

Data Analytic Plan. Baseline demographics and EC attitudes, intentions, and use will be summarized by groups as appropriate. Continuous variables will be presented as mean±SD and

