compared among the 2 groups using ANOVA test. Categorical variables will be presented as counts and proportions and compared among the 2 groups using the chi-squared test. EC trial and use, at baseline and 6-month follow-up, will be compared between the 2 groups using logistic regression analysis. The GEE model will be performed for the repeated measure analysis of EC attitudes, intentions, and use across multiple visits. Self-reported exposure and receptivity to other tobacco advertising will be used as a covariate in the analyses.

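### The GEE for the EC attitude and intention scales does not list each scale's own baseline score as a covariate; adding it would gain precision on non-primary outcomes

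*Combined protocol and SAP*

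**What the plan says.** All references are to the combined protocol and SAP.

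- **Model.** The Data Analytic Plan states: "The GEE model will be performed for the repeated measure analysis of EC attitudes, intentions, and use across multiple visits". It adds: "Self-reported exposure and receptivity to other tobacco advertising will be used as a covariate in the analyses". It names no other covariate, and gives no link function, working correlation or arm contrast.
- **Stated use of baseline scores.** The same section says: "Baseline demographics and EC attitudes, intentions, and use will be summarized by groups as appropriate". A between-group comparison by ANOVA or chi-squared follows. No other use of the baseline scale scores is given.
- **Availability.** Under Procedures, "participants will come to the lab for a baseline visit and complete sociodemographic questions and measures pertaining to tobacco use susceptibility"; severity, motivation and intentions are listed in the same sentence, and randomisation comes after this visit. The scales are repeated later: "At the one month, three month, and six month marks, participants will come into the lab and be assessed for tobacco use susceptibility", again with the other scales.
- **Aim.** The R00 Phase: Aim 2 text says "I will track participant changes over 6 months in the following measures: susceptibility, severity, behavioral intentions, and actual tobacco use behavior". Measures says: "Motivation to avoid ECs including importance, confidence, and readiness to avoid ECs will be collected to assess for changes in motivations". Both speak of change, but neither defines a contrast.
- **Status.** Power Analysis makes trial of EC products the primary outcome, so the scales are non-primary.

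**The concern.** A scale's own earlier value is often its best single predictor. Here it is measured before randomisation, so conditioning on it does not bias the arm comparison, and in a linear model it can narrow the interval. The plan names two advertising covariates and omits this one.

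As written, the sentence admits several models: follow-up visits only; arm-by-visit change with the arms free to differ at baseline; baseline as a response with a common mean in both arms; or baseline as a covariate. The first two are unbiased but do not use the baseline score fully. At stake is the width of the intervals on susceptibility, severity, motivation and intentions, with about 60 per arm after attrition, and a choice of model that could otherwise be made after the data are seen. Reading EC attitudes as these scales is an assumption; the Data Analytic Plan does not list them.

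**Working it through.** **The plan's own figure.** Inputs from Power Analysis: 24% versus 6%, two-sided 0.05 chi-squared test, 75 per arm enrolled, 20% attrition, so 75 × 0.8 = 60 per arm. Null SE = sqrt(2 × 0.15 × 0.85/60) = 0.0652. Alternative SE = sqrt((0.24 × 0.76 + 0.06 × 0.94)/60) = 0.0631. Power = Φ((0.18 − 1.96 × 0.0652)/0.0631) = 79.6%. The stated 80% reproduces, and nothing below enters it.

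**Assumptions for the scales.** The documents give no SD or correlation. I take unit SD, a linear outcome, 60 per arm with complete data, and baseline to month-6 correlation r. The named covariates are first taken as not prognostic.

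**Month-6 contrast.** Variance per participant:
- follow-up only: 1
- change: 2(1 − r)
- conditioned on baseline with its own month-6 slope: 1 − r²

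SE = sqrt(2 × variance/60); reduction = 1 − sqrt(variance ratio).

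| r | SE follow-up only | SE change | SE conditioned | Reduction vs follow-up only | Reduction vs change |
|---|---|---|---|---|---|
| 0.2 | 0.183 | 0.231 | 0.179 | 2% | 23% |
| 0.4 | 0.183 | 0.200 | 0.167 | 8% | 16% |
| 0.7 | 0.183 | 0.141 | 0.130 | 29% | 8% |

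Below r = 0.5 a change contrast is less precise than ignoring baseline. In 20,000 simulated trials the reductions were 1.5/8.1/27.7% and 22.2/16.2/7.3%, slightly lower because the slope is estimated.

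**If the named covariates are prognostic.** Suppose their baseline values together correlate 0.4 with the scale at every visit. Put s = 1 − 0.4² = 0.84 and c = r − 0.16. The variances become s, 2(s − c) and s − c²/s. At r = 0.2/0.4/0.7 the reductions are 0.1/4/23% versus follow-up only and 28/20/9% versus change.

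**Three-visit average.** With equal correlation between all visits, the variances are (1 + 2r)/3; that plus 1 − 2r for change; and that minus r² when conditioned. At r = 0.2/0.4/0.7 the SE reductions are 4/14/38% versus follow-up only and 37/26/12% versus change.

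**Unequal correlations.** One baseline slope shared by all visits equals the average b of the three baseline-to-visit correlations, so the month-6 variance is 1 − 2b·r6 + b², where r6 is the month-6 correlation.
- Assumed 0.7/0.5/0.2: b = 1.4/3 = 0.467; variance 1 − 0.187 + 0.218 = 1.031; SE 0.185, against 0.183 for follow-up only and 0.179 with a visit-specific slope. Simulation gave 0.187 to 0.188, 0.184 and 0.181.
- Assumed 0.7/0.5/0.3: b = 0.5; variance 0.95; the gain is 2.5% instead of 5%.
- Assumed 0.6/0.5/0.4: b = 0.5; variance 0.85; the gain is about 8%, nearly intact.

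In the first case the three-visit average still gains: simulated SE 0.129 against 0.152.

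**Baseline as a response with a common mean.** When the true correlation is exchangeable, an exchangeable working correlation gives month-6 variance 0.96/0.84/0.51 at r = 0.2/0.4/0.7, the same as conditioning. Independence gives 1.00 throughout, so no gain. In the steep-decline case above, with correlations between follow-up visits of 0.7/0.6/0.4, the exchangeable version gave SE 0.190, worse than follow-up only. An unstructured working correlation lets each visit have its own baseline correlation.

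**The case against.** The strongest objection is that this is a preference among valid models in a brief plan. The follow-up-only and change models are unbiased, the documents contain no error or contradiction here, and every figure for the gain rests on assumed correlations. It adds that a single baseline term can fail to help at month 6, and that precision is gained without cost only on a linear scale.

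Much of this stands. The gain against follow-up only is close to nil at low r. Enrolment also selects on susceptibility ("The sample will include young adults who are susceptible to using ECs"), which may lower r for that scale. The single-slope objection is correct and is why the fix carries a baseline-by-visit term. The link objection is also correct: under a logit link, adjustment changes the odds ratio being estimated. The covariate figures assume baseline values, whereas exposure and receptivity are also asked weekly after randomisation and the plan does not say which values it will use.

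What does not stand is that the choice is immaterial. Power Analysis itself relies on longitudinal models to raise power, and how much they do so for the scales depends on the choice left open.

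A reader might infer that the plan commits to ignoring baseline. The text does not say so: baseline could be one of its multiple visits. A reader might also infer bias; none arises under the models considered.

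**Conclusion.** The point holds as a minor efficiency improvement on non-primary outcomes. The pre-randomisation scores are collected, and the plan gives them no stated role in the GEE. For linear scale scores with 60 per arm, non-prognostic named covariates and r from 0.2 to 0.7, conditioning on baseline lowers the month-6 SE by about 2% to 29% versus follow-up only and 23% to 8% versus change. These figures require visit-specific baseline slopes, or equal correlations across visits.

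Two stronger readings are not supported. A reader might infer that any form of baseline adjustment brings the whole gain at no cost; the unequal-correlation, working-correlation and link results show otherwise. A reader might also infer that the trial's power is in doubt; EC trial is analysed separately and its 80% stands. Nor does the point extend to EC use in the same GEE sentence: under Participant Recruitment and Screening every entrant has never tried an e-cigarette, so there is no baseline EC use to adjust for.

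**What to change.** Add to the Data Analytic Plan, for scales analysed as continuous with an identity link:

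- Responses are months 1, 3 and 6; baseline is not a response visit.
- Terms are arm, visit, arm-by-visit, the scale's own baseline score and baseline-by-visit, plus the named advertising covariates.
- Report the three-visit average and the month-6 arm contrasts.
- Name the scales that EC attitudes covers, and state the link and working correlation.

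As an alternative, keep baseline as a response with a common mean across arms and an unstructured working correlation.

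The cost is SAP wording and three baseline slopes per model (one per follow-up visit). No new data, visits or participants are needed.

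### Does leaving the time point of the advertising covariates unstated put the comparison of arms at risk of adjustment for a post-randomisation variable?

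*Combined protocol and SAP*

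**What the plan says.** The covariate rule is one sentence at the end of the Data Analytic Plan: "Self-reported exposure and receptivity to other tobacco advertising will be used as a covariate in the analyses". It follows the two models it appears to govern, a logistic regression for e-cigarette trial and use, and a GEE: "The GEE model will be performed for the repeated measure analysis of EC attitudes, intentions, and use across multiple visits".

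The Procedures section describes two occasions of measurement.

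- **Baseline visit.** The battery includes "exposure to tobacco advertising,^{24,25} and receptivity to tobacco advertising", with an instrument reference for each. Allocation comes afterwards: "Then, participants will be randomized in a 1:1 ratio to one of two conditions using a computer-generated sequence".
- **Weekly, after allocation.** The delivery schedule is: "Every week, for 24 weeks, participants will be instructed to view a 10-page online magazine". At each issue: "Before viewing, participants will be asked about their exposure to tobacco advertising in the last week and their receptivity to advertising". These items sit alongside masking questions. On content: "Every magazine will also contain two EC ads and two ads for products other than tobacco".

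The batteries listed for the 1-, 3- and 6-month lab visits include neither measure. The Measures section describes the instruments, including "tobacco advertising receptivity, a validated measure of tobacco promotional product influence", without saying when they are given.

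**The concern.** The intervention is itself advertising, so a measure of response to advertising taken during follow-up could lie on the path from assignment to outcome. From the second magazine on, the weekly items are answered after participants have been sent the assigned ads. If the unregulated ads raise receptivity, and receptivity raises the chance of trying an e-cigarette, then a model holding weekly receptivity fixed no longer estimates the total effect of assignment. The adjusted arm effect on the primary outcome would move towards the null.

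Because the plan names no time point, an analyst could choose either version, possibly after seeing the data. The planned sample size has almost no spare power to absorb a loss.

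**Working it through.** **1. The plan's own power figure.** Inputs from the Power Analysis: 24% v 6%, two-sided 0.05 chi-squared test, 150 enrolled, 20% attrition, so 150 × 0.8 = 120, or 60 per arm.

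- Mean rate: (0.24 + 0.06)/2 = 0.15.
- Null SE: √(2 × 0.15 × 0.85/60) = 0.0652.
- Alternative SE: √((0.24 × 0.76 + 0.06 × 0.94)/60) = 0.0631.
- Power: Φ[(0.18 − 1.96 × 0.0652)/0.0631] = Φ(0.83) = 79.6%.

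This reproduces the stated 80%. No covariate enters it, so the choice of time point changes no figure in the plan.

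**2. Which measurement does the covariate sentence describe?**

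| Feature | Baseline items | Weekly items |
|---|---|---|
| Taken before allocation | Yes | No |
| Receptivity item refers to tobacco | Yes | No, advertising in general |
| Instrument cited | Yes | No |
| One value per person | Yes | No, up to 24, with no rule to reduce them |
| Fits a model indexed by visit | Yes, as a fixed covariate | No stated link from weeks to visits |

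The covariate sentence speaks of tobacco advertising, which for receptivity matches the baseline item better. A single 6-month logistic model needs one value per person, and only baseline supplies that without a further rule. The GEE runs over visits, and the follow-up visits do not list these measures.

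**3. Size of the harm if weekly values were used.** The documents give neither a shift in receptivity nor its link with trial, so every input here beyond the rates and the 60 per arm is an assumption. Let the covariate X have SD 1 and mean *s* in the unregulated arm, 0 in the regulated arm. Let logit P(trial) = a + d × arm + b × X, with a and d set so that the overall rates stay at 6% and 24%. The unadjusted odds ratio is (0.24/0.76)/(0.06/0.94) = 4.95.

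With *s* = 0, the arm odds ratio given X is 5.42 for b = 0.7 and 5.98 for b = 1.0. These exceed 4.95 only because the odds ratio is non-collapsible. Holding the marginal rates fixed means d + b × s is constant, so the adjusted odds ratio at shift *s* is the *s* = 0 value × exp(−b × s). For example, 5.42 × exp(−0.7 × 0.3) = 4.39. Power is for the likelihood-ratio test of arm, from 20,000 simulated trials per scenario; the unadjusted test has 84%.

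| Shift (SD) | Adjusted OR, b = 0.7 / 1.0 | Adjusted power |
|---|---|---|
| 0 | 5.4 / 6.0 | 85–87% |
| 0.1 | 5.1 / 5.4 | 82% |
| 0.2 | 4.7 / 4.9 | 78% |
| 0.3 | 4.4 / 4.4 | 71–74% |
| 0.5 | 3.8 / 3.6 | 57–63% |
| 0.8 | 3.1 / 2.7 | 36–47% |

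The zero-shift row also stands for a baseline covariate, if the baseline value predicts trial as strongly as a later one would. If it predicts less well, the 1–3 point gain over 84% shrinks, but no bias appears.

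**4. Exposure taken separately.** The covariate is exposure to *other* advertising, and both arms receive two e-cigarette ads per issue. Even if participants counted the study ads in the weekly item, the number delivered is equal. A difference between arms would need differential opening, noticing or recall, and the documents give no evidence of that.

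**The case for a change.** The strongest case for a change is that the text really is silent and the covariate enters the primary model. The weekly items have no other stated analytic use, and a GEE can take time-varying covariates. The word *other* does not settle it, since the weekly exposure item, as described, does not exclude study ads, and the word says nothing about whether receptivity responds to assignment. Receptivity is described as a measure of promotional influence, so mediation is plausible. Recording the choice would cost a sentence.

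Part of this stands. The time point is missing, the difference in wording between the two receptivity items could be loose drafting, and adjustment for an affected weekly value would be wrong for the total effect.

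The arguments for expecting that analysis are weaker. Having no stated analytic use does not single out the weekly items: time on the ad page, ad recall and cotinine have no role in the Data Analytic Plan either, and the weekly items may serve partly as masking. A GEE accepts baseline covariates equally well. Mediation cannot be judged, because the receptivity items are not shown. The large losses in the illustration need shifts of 0.5–0.8 SD; at 0.1–0.2 SD the loss is 2–6 points against the unadjusted 84%.

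**Conclusion.** No change to the plan is called for. The covariate sentence omits a time point, and that is certain from the text. What the plan does state, however, does not produce a wrong result. The reading that best fits its wording and models is baseline values, which cause no bias from this source and may add a little precision. An analyst following ordinary practice for a randomised comparison would use them.

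Bias would require all three of these: use of weekly values, a shift in receptivity that differs between arms, and an association of receptivity with trial. None is established, and the mechanism is weak for exposure. The possible loss runs from 2 points of power at a 0.1 SD shift to between 37 and 48 points at 0.8 SD (84% down to 36–47%), all resting on an assumed covariate effect of 0.7–1.0 log-odds per SD. Confidence is high that the time point is unstated and low that any bias would follow.

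### The primary logistic model for EC trial omits the baseline EC susceptibility score already collected before randomisation; adding it is a cheap, modest improvement, not the correction of an error

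*Combined protocol and SAP*

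**What the plan says.** The Power Analysis section fixes the primary outcome: "Trial of EC products is the primary outcome of the study; thus estimated power will be based on this outcome at the 6-month follow-up". It assumes that trial rates "will be higher in both the unregulated (24%) and regulated (6%) groups", and sizes the study "to detect an 18% difference in increased trial of EC products between unregulated and regulated groups" with a two-sided 0.05 chi-squared test. It enrols 75 per group and expects 120 participants in total after 20% attrition.

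The Data Analytic Plan names the model: "EC trial and use, at baseline and 6-month follow-up, will be compared between the 2 groups using logistic regression analysis". Its only statement on adjustment is "Self-reported exposure and receptivity to other tobacco advertising will be used as a covariate in the analyses". No other covariate is named.

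The Procedures section has participants "complete sociodemographic questions and measures pertaining to tobacco use susceptibility" at the baseline visit, and randomisation follows. The Measures section gives the susceptibility instrument as a 27-item measure that includes ECs. Susceptibility to ECs is also a condition of entry. Randomisation is described only as a 1:1 computer-generated sequence, with no stratification.

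**The concern.** Entrants must never have tried an e-cigarette, so the outcome has no baseline value to adjust for. Among the baseline measures, susceptibility is an obvious candidate to predict later trial. It is already paid for, is measured before allocation, and neither the design nor the model uses it.

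The stakes are modest but not nil. The study has no spare power at its own assumptions and expects few events. Without stratification or adjustment, a chance difference between the arms in susceptibility passes straight into the primary estimate. Adding the covariate after seeing such an imbalance would be open to challenge, so the choice has to be prespecified.

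A smaller matter of scale goes with this. The study is powered on a difference in proportions, while the covariate-adjusted logistic model delivers a conditional odds ratio.

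**Working it through.** **Inputs from the documents.** Rates 24% and 6%; two-sided 0.05 chi-squared test; 75 per group enrolled; 20% attrition, so 75 × 0.8 = 60 per group analysed.

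**1. The plan's own power.** Pooled rate (0.24 + 0.06)/2 = 0.15.
- SE under the null: √(2 × 0.15 × 0.85/60) = 0.0652.
- SE under the alternative: √((0.24 × 0.76 + 0.06 × 0.94)/60) = 0.0631.
- Power = Φ((0.18 − 1.96 × 0.0652)/0.0631) = Φ(0.828) = 79.6%. Exact enumeration of the Pearson test gives 81.4%.
- For 80% power the same formula needs 61 per group; 61/0.8 rounds up to 77 per group, or 154 in all, against 150 planned.

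The stated 80% reproduces and uses no covariate.

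**2. Information available.** Expected events: 60 × 0.24 + 60 × 0.06 = 14.4 + 3.6 = 18. If exposure and receptivity take one term each, the planned model has three terms including arm (18/3 = 6 events per term). With susceptibility it has four (18/4 = 4.5).

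**3. Effect of adding susceptibility.** Its prognostic strength is not in the documents, so a range is assumed. Simulation: 60 per arm; marginal rates held at 24% and 6%; standard-normal score; two advertising covariates with an assumed odds ratio (OR) of 1.3 per SD each; 8,000 runs per row (Monte Carlo error about 0.4 points on each power figure). Each cell shows the planned model, then the planned model plus susceptibility.

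| Assumed OR per SD | Likelihood-ratio power | Wald power | Median SE of log OR | Variance ratio, risk difference |
|---|---|---|---|---|
| 1.0 | 83.2% → 83.0% | 77.5% → 77.4% | 0.664 → 0.668 | 1.008 |
| 1.5 | 83.5% → 84.2% | 78.1% → 79.0% | 0.663 → 0.674 | 0.991 |
| 2.0 | 83.4% → 85.4% | 78.3% → 80.2% | 0.663 → 0.689 | 0.957 |
| 2.5 | 84.1% → 86.6% | 78.4% → 81.2% | 0.663 → 0.706 | 0.928 |
| 3.0 | 83.1% → 87.2% | 77.8% → 82.3% | 0.662 → 0.729 | 0.894 |

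The gain runs from none to about 4 points (likelihood ratio) or 4.5 points (Wald). The standard error of the log OR rises in every row. Power still improves because the conditional OR moves further from 1. The marginal OR is (0.24/0.76)/(0.06/0.94) = 4.95. If the arm intercepts are solved so that the logistic curve, averaged over a standard-normal score, returns 24% and 6%, the OR conditional on susceptibility alone is 5.4 at OR 2 per SD and 6.2 at OR 3.

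**4. Chance imbalance.** The difference between arm means of a standardised score has SD √(2/60) = 0.183. An imbalance of 0.3 SD or more therefore has probability 2 × (1 − Φ(0.3/0.183)) = 10%. Shifting the arms by ±0.15 SD moves the expected unadjusted difference from 18 points to 15.7 or 20.3 at OR 2, and to 14.7 or 21.4 at OR 3.

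**5. Type I error.** Null rate 15% in both arms, susceptibility OR 2.0, other settings as in step 3: likelihood-ratio 5.7% → 6.1%, Wald 4.4% → 4.6%. With the advertising covariates unrelated to trial, a separate likelihood-ratio simulation gave 5.1% with and without the score.

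**6. Replacing the advertising covariates instead of adding to them.** Likelihood-ratio power, 4,000 runs, susceptibility OR 1.5 (Monte Carlo error about 0.6 points):

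| Advertising covariates | Planned covariates | Susceptibility alone |
|---|---|---|
| Unrelated to trial | 83.2% | 83.8% |
| OR 1.5 each | 84.4% | 83.6% |
| OR 2 each | 86.8% | 83.5% |

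Replacement gains nothing measurable in the first case and loses about 1 to 3 points in the others.

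**The case against.** The strongest reply is that nothing here is broken. In a randomised trial, leaving out a prognostic covariate does not bias the unadjusted risk difference or invalidate the test, and the sample size was justified without adjustment. That stands, and it makes this an efficiency suggestion.

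A reader might infer from the selection rule that susceptibility must be strongly prognostic and that the plan discards free power and precision. The documents do not support this, for three reasons.
- They give no strength of association. Restricting entry to susceptible never-users narrows the range of the score and may weaken prediction within the sample, whereas the simulation uses an unrestricted score. The instrument also covers tobacco products generally.
- Precision improves only for a marginal estimate such as the standardised risk difference.
- The term is not free with about 18 events, of which only 3.6 are expected in the regulated arm.

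A reader might also infer that the advertising covariates are weak and could be swapped out. Nothing in the documents shows that, and the Measures section describes the receptivity instrument as validated.

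Two further objections carry some weight. Intentions, severity and motivation are also measured at baseline, so preferring susceptibility is a judgement. And the chi-squared test and the logistic model address the same null hypothesis, so the risk difference is a reporting matter. It is still the scale on which the study was powered.

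**Conclusion.** The omission is real, and prespecifying the score is worthwhile, but the benefit is small and rests on an assumption. At OR 1.5 per SD the power gain is under 1 point, close to simulation error. At OR 2 it is about 2 points and at OR 3 about 4 to 4.5. The variance of the standardised risk difference falls by about 1%, 4% and 11% respectively. If the score is not prognostic among those enrolled, the cost is a negligible loss of power and about 1 to 2% more variance. Protection against chance imbalance is the other benefit, and it too depends on the score being prognostic. These figures assume the plan's rates of 24% and 6%, 60 analysed per arm, and a roughly normal score entered linearly. The stated power and sample size are unaffected.

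**What to change.** In the Data Analytic Plan, write: 'The month-6 EC trial comparison will be adjusted for the continuous baseline (pre-randomisation) EC susceptibility score, as a single term, in addition to baseline exposure and receptivity to tobacco advertising. The standardised risk difference with 95% CI will be reported alongside the odds ratio.' State how the EC score is formed from the 27-item measure.

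Naming baseline values also closes a gap in the present covariate sentence: exposure and receptivity are asked again each week after randomisation, and the plan does not say which time point enters the model. Do not drop the advertising covariates on the assumption that they are weak.

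Cost: two sentences of analysis wording, with no new data, visits or participants. The downside is one more model term with about 18 expected events, a rise in likelihood-ratio type I error of at most about 0.4 points in simulation, and the small variance penalty above if the score proves uninformative.
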